## ADVERSE EVENTS

### Adverse Event Definitions

An **adverse event** (AE) is any untoward medical occurrence in a study subject, regardless of the relationship between the adverse event and the device under investigation. All AEs experienced by all subjects will be documented throughout the entirety of the study, as outlined below.

In this study, the subjects will be instructed to report AEs spontaneously or in response to general, non-directed, or directed questions. At any time during the study, the subject may volunteer information that resembles an AE. Once it is determined by trained study personnel confirming with the subject that an AE has occurred, the investigator will obtain all the information required to complete the AE form. Any medical management of an event and the date of resolution of the event must be recorded on the appropriate eCRF using medical terminology. Any AE experienced by a subject will be followed until the AE has resolved to the clinical investigator's satisfaction or is considered stable. If information about an AE (or suspected AE) is not adequately obtained via incoming calls to Customer Technical Support or electronic means, the study team will contact the participant, request medical records and/or contact the subject's physician for more information. Trained study personnel will follow Tandem's Customer Technical Support working instructions (WIA-000005) for customer outreach policies when confirming an adverse event for the study. The adverse event form will document the following:

- AE diagnosis or definition
- Serious/non-serious
- Severity
- Action taken
- Relationship to Control-IQ System
- Anticipated/Unanticipated
- Date of onset
- Date of resolution

Additional information on specific events may be recorded in the eCRF.

Each adverse event form that has been verified will be reviewed by the clinical investigator to determine the type, intensity, severity, and causality of the event, and whether anticipated or unanticipated, in order to verify the reporting that is required. The guidelines below will be followed to characterize each event.

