	
participants were fully CGM naive, adjusted CGM naive target goals for children to represent current number enrolled in study (n=18).
 
Changed 6-9 years old enrollment goal to 163, as recently published data of 30 children age 6-9 shows successful use of Control-IQ technology (10).
 
Clarified that all reported Adverse Events must be verified by trained study personnel prior to entry into the eCRF and that all outreach attempts to participants follow Tandem's Customer Technical Support customer outreach procedure WIA-000005.
 
Removed the specific section reference within QS-045.
 
Updated Appendix C to be consistent with Tandem's Customer Technical Support customer outreach procedure WIA-000005.

--	---

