Periodic Data Collection procedures	
100% of calls to Tandem Customer Technical Support will be screened for reportable AEs based on the definitions of SH and DKA included in this protocol. Outreach surveys will be deployed to all study participants: Monthly to collect AE incidence, and at 3, 6 and 12 months to collect other PROs (See Table 1).

Management of Adverse Events	
Safety information will be collected on an ongoing basis throughout the study as Tandem becomes aware of device-related AEs. These events will be recorded electronically from both inbound reports from customers and assessed through outreach to patients. The event, date of onset, severity, seriousness, duration and relationship to the device will be documented. All reported device-related AEs will be followed until they are adequately resolved or stabilized, until study completion/termination, or until number of outreach attempts made by clinical personnel corresponds with company's Customer Technical Support policy for adverse and device issue event outreach, whichever comes first. Safety events will be summarized based on FDA codes.

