**Table 1: Timeline of Data Collection**

Procedure/Assessment	Baseline*	Monthly	Months 3 and 6	Final
Informed Consent	X			
**Release of medical records				
Screening for eligibility	X			
Report of incoming AEs		X		X
Outreach for AEs	X	X		X
User Experience	X		X	X
Psychosocial Outcomes	X		X	X

\*Includes demographics, frequency of AEs

\*\*Only requested as needed to collect additional information on reported AEs

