#### **Enrollment procedure:**

The enrollment process has been detailed in the flowchart in **APPENDIX A**. Study subjects will be enrolled using customer recruitment filters and triggers from two data sources housed within Tandem – (a) the CRM (or the Custom Relationship Management Technology) and (b) the t:connect® customer portal (web secure application designed for Tandem users to request prescriptions for any pump-related updates and complete necessary trainings). Daily automatic recruitment invite contact lists, defined by study inclusion and exclusion criteria, will be generated for eligible Tandem users and using a

secure file transfer protocol, and Qualtrics (a HIPPA compliant survey and report generating software) will deploy automated survey invites daily (via email or SMS text). The first study invite will include important information about the study eligibility criteria and an invitation to start the informed consent process, including a Release of Medical Records form and the baseline questionnaires (baseline adverse events and other PRO measures). Tandem users who indicate that they are not interested in participating will be removed from the potential recruitment list and will not receive any further communication about the study. The remaining users will receive reminder emails (as needed) and those interested will complete the IRB approved electronic consent form by providing their digital signature.

**Duration of therapy and follow-up:** All enrolled subjects who initiate therapy with the Control-IQ System will be monitored from baseline through 12 months following the initiation of treatment. Participants will be considered screen failures if Control-IQ data has not been downloaded to t:connect 120 days after the baseline survey's completion.

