Participants already recruited during the COVID emergency who did not have a recent HbA1c result within the past 6 months of enrollment will not be counted toward overall recruitment goals, and will be analyzed separately.

**Observation and Recording of Adverse Events:** Subjects will be required to report AEs. Open-ended questions and questions specific to SH and DKA will be included in all subject outreach contacts. In addition, the Global Post-market Surveillance data base (Tandem Diabetes Care, Inc.) will be queried monthly to determine the incidence of SH and/or DKA reported by study subjects (see **APPENDIX C** for surveillance procedures).

An AE form will be completed for every adverse event reported by a subject and verified by trained study personnel. Any medical management of an event and the resolution of the event must be recorded within the internal database utilized by Tandem's Global Post-

market Surveillance team (CRM), as the source documentation, and on the appropriate eCRF using medical terminology.

**Patient-reported Outcomes:** Questionnaires and surveys suitable for subjects being treated for type 1 diabetes (see **APPENDIX D**) will be electronically deployed to subjects at times specified in the Data Collection Timeline.

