#### **Diabetic ketoacidosis:**

DKA is reportable as an adverse event when the subject reports the following:

- Symptoms such as polyuria, polydipsia, nausea or vomiting, and
- Treatment provided in a health care facility, and
- Diagnosis of DKA made by a health care provider and self-reported by the patient.

Subjects will be instructed on this specific definition of DKA each time information is requested related to this AE.

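### SH and DKA reports become AE records only after verification, and no rule says how a report that cannot be verified is counted in the primary rate

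*Combined protocol and SAP*

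**What the plan says.** All references are to the combined protocol and SAP.

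- **Verification step.** Under Adverse Event Definitions, the investigator collects the AE form information "Once it is determined by trained study personnel confirming with the subject that an AE has occurred". Under Observation and Recording of Adverse Events: "An AE form will be completed for every adverse event reported by a subject and verified by trained study personnel". The Protocol Revision History gives the intent of version 07 in matching terms: "all reported Adverse Events must be verified by trained study personnel prior to entry into the eCRF".
- **Other sources.** If information on an AE or a suspected AE is inadequate, Adverse Event Definitions adds that "the study team will contact the participant, request medical records and/or contact" the physician.
- **Records release.** Both data collection schedules footnote the release form: "Only requested as needed to collect additional information on reported AEs". The Enrollment procedure instead puts it in the first invitation and consent step, "including a Release of Medical Records form and the baseline questionnaires".
- **End of follow-up.** The Synopsis (Management of Adverse Events) lets follow-up of device-related AEs end on resolution, at study end, "or until number of outreach attempts made by clinical personnel corresponds with company's Customer Technical Support policy". Adverse Event Definitions follows any AE until it is resolved or stable and names no attempt limit. It does apply the sponsor's customer outreach instruction to the confirmation step.
- **Endpoint definition.** "DKA is reportable as an adverse event when the subject reports the following": symptoms, treatment in a facility, and a provider's diagnosis that the patient self-reports. Subjects are given the SH and DKA definitions each time they are asked.
- **Success criterion.** Under Primary Outcome, SH and DKA incidence must be no higher than the literature rates.

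**The concern.** The primary numerator is a count of AE records. A participant may report DKA in a monthly survey, with answers that already satisfy the protocol's DKA definition, and then stop responding. The definition would count that report. The AE form rule would not, because the report is unverified. No section settles the conflict, so two analysts could count the same report differently.

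The gap lies in the primary safety endpoint. The criterion is met when the rate is not high, so each true event left out moves the result toward success. If the participant's observed time stays in the denominator, nothing offsets the loss. The plan expects 25% attrition, so disengagement is foreseen, and people may be hardest to reach after a serious event. This differs from ordinary survey non-response, because here the sponsor already holds a report.

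**Working it through.** **1. Follow one report through the text.**

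| Step | What the plan provides |
|---|---|
| Report arrives by survey, support call or surveillance query | Captured |
| Staff confirm with the subject | Needed before the AE form |
| Subject unreachable | Records or physician may be used |
| Access to records | Release requested after the report (schedules) or at consent (Enrollment procedure) |
| Outreach attempts used up, still unverified | No classification and no counting rule |

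The last row is the gap. The AE form is for verified events, so the natural result is omission, although no section states it.

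**2. The plan's own figure.** The Synopsis expects 1,547 completers after 25% attrition: 1,547 / 0.75 = 2,062.7, which rounds up to the stated 2,063. (Step 3 of Determination of Sample Size gives 1,354 completers; 1,354 / 0.75 = 1,805.3, which does not lead to 2,063.) I use 1,547 patient-years, one year per completer.

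**3. Inputs for the illustration.**
- Benchmarks from Determination of Sample Size: SH 25.35 and DKA 11.03 per 100 patient-years.
- Test from Statistical Analysis: one-sample exact binomial, two-sided, alpha 0.05, taken here as 2.5% per tail.
- Loss f, the share of true events reported but never verified and not counted. The documents give no value, so 0, 5, 10 and 20% are assumed.

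Expected counts at benchmark: SH 1,547 × 0.2535 = 392.2; DKA 1,547 × 0.1103 = 170.6.

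Smallest count that is significantly high: SH 427 (binomial) or 432 (Poisson); DKA 196 or 198.

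**4. Effect on detecting a true 20% excess.** The expected observed count is benchmark count × 1.2 × (1 − f). Power is the probability of reaching the critical count. Both models are shown because the plan tests a rate per patient-year as a binomial proportion, while repeat events would be counts.

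| f | SH expected count | SH power, Poisson | SH power, binomial | DKA expected count | DKA power, Poisson | DKA power, binomial |
|---|---|---|---|---|---|---|
| 0 | 470.6 | 97% | 99% | 204.8 | 69% | 75% |
| 5% | 447.1 | 77% | 88% | 194.5 | 41% | 47% |
| 10% | 423.5 | 35% | 43% | 184.3 | 16% | 19% |
| 20% | 376.5 | 0.3% | 0.2% | 163.8 | 0.5% | 0.5% |

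A 20% excess is fully masked, in expectation, when 1 − 1/1.2 = 16.7% of events are lost.

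**5. Small losses.** At f = 2%, binomial power for the SH excess is still 97%. The gap matters only if the unverifiable share reaches several percent of true events.

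**The case against.** The strongest reply is that the plan has more safeguards than the confirmation sentence suggests.

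- **Sources other than the subject.** A reader might infer that only the subject can confirm an event. The same section allows records and physician contact for a suspected AE, and the investigator responsibilities repeat this. That reading fails. What stands is that, under the schedules, the release is sought only after a report, possibly from someone no longer reachable. The Enrollment procedure says otherwise, and the consent form is not in the reviewed text, so access cannot be settled.
- **Withdrawal and death.** A reader might infer that these events simply vanish. Subject Withdrawal or Termination keeps data collected before withdrawal in the analyses, and death is a reportable SAE. Only a report still unverified at that point is at risk. No section names family as an accepted source, however, and the DKA definition requires self-report.
- **Silence is not exclusion.** No sentence says that unverified reports are discarded. The outreach limit ends follow-up; it does not void a report. The monthly surveillance query is a second way to find reports, but it does not lift the verification condition on the AE form. A rule may exist in Appendix C, in the outreach instruction or in the separate analysis plan that the protocol promises. None of these can be seen here.
- **Direction.** A reader might infer that the rate is biased downward. Verification also removes false reports, such as lows treated with help but without altered consciousness, and the documents do not say whether the benchmark events were verified. The net direction is not established.
- **Definition versus check.** A reporting definition and a verification step can coexist. That is fair, but the plan must still say which governs when the check cannot be completed.

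**Conclusion.** The point holds as a missing rule with a plausible, unquantified effect on the primary endpoint. AE form entry depends on verification, and no section classifies an SH or DKA report that remains unverified. Read literally, that report cannot reach the primary rate, even if it already meets the DKA definition. True events lost this way would favour the success criterion.

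The documents do not support saying that such events are discarded, that confirmation rests on the subject alone, or that the rate is biased downward. The power figures rest on assumed losses, on 1,547 patient-years, and on a true rate 20% above benchmark. They show sensitivity and do not estimate what will happen. This is a should-fix: cheap to close, and able to change what the study can conclude.

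**What to change.** 1. Under Observation and Recording of Adverse Events and Adverse Event Definitions, open a record at first report with a status of confirmed, refuted or unverifiable (unreachable, withdrawn, deceased).
2. Report the number of unverifiable SH and DKA reports.
3. Present each rate twice: confirmed events only, and with unverifiable reports that meet the protocol's SH or DKA definition added as events. State whether the Primary Outcome conclusion holds under both. Which of the two is primary is a trade-off for the sponsor to settle in advance.
4. Name a parent, family member or health-care provider as an acceptable source when the subject cannot be reached or has died.
5. Reconcile the Enrollment procedure with the two schedules on when the records release is obtained, and the Synopsis with Adverse Event Definitions on when follow-up ends.

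The cost is protocol wording, one eCRF status field and a second tabulation, with no new participant contacts. Some false-positive reports will enter the second rate and make it slightly less favourable; the confirmed-only rate beside it bounds that effect.

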### **Reportable Adverse Events:**

For this protocol, a reportable adverse event includes any untoward medical occurrence that meets one of the following criteria, as defined below:

1. Hypoglycemia meeting the definition of severe hypoglycemia (SH)
2. Diabetic ketoacidosis (DKA)
3. A serious adverse event (SAE)
4. An adverse device effect (ADE)

Hypoglycemia and hyperglycemia not meeting the criteria below will not be recorded as adverse events unless associated with an adverse device effect (ADE). Skin reactions from sensor placement are only reportable if severe and/or if they required treatment.

#### **Severe Hypoglycemia:**

Hypoglycemia not associated with an ADE is only reportable as an adverse event when the assistance of another person was required in order to actively administer carbohydrate, glucagon, or other resuscitative actions due to altered consciousness. This means that the subject was impaired cognitively to the point that he/she was unable to treat him/herself, was unable to verbalize his/her needs, was incoherent, disoriented and/or combative, or experienced seizure or coma. These episodes may be associated with sufficient neuroglycopenia to induce seizure or coma. If glucose measurements are not available during such an event, neurological recovery attributable to the restoration of glucose to normal is considered sufficient evidence that the event was induced by a low glucose concentration.

Subjects will be instructed on this specific definition of severe hypoglycemia each time information is requested related to this AE.

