#### **Serious Adverse Event (SAE):**

In accordance with 21 CFR Parts 803 and 812, a SAE is defined as any untoward medical occurrence that:

- Results in death,
- Is life-threatening,
- Requires hospitalization or prolongation of existing hospitalization,

- Results in persistent or significant disability/incapacity or substantial disruption of the ability to conduct normal life functions,
- Is a congenital anomaly or birth defect, or
- Is considered a significant medical event by the investigator based on medical judgement (e.g., may jeopardize the subject or may require medical/surgical intervention to prevent one of the outcomes listed above).

Medical and scientific judgement will be exercised in deciding whether medical events that may not be immediately life-threatening or result in death or hospitalization, but may jeopardize the subject or may require intervention to prevent one of the other outcomes listed in the definition above, should also be considered serious. A serious adverse event must be reported to the FDA as soon as possible, within a maximum of 15 calendar days.

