**Adverse Device Effect (ADE):**

Any untoward medical occurrence in a study subject which the device may have caused or to which the device may have contributed (Note that a Device Deficiency or Issue Form must be completed in addition to an Adverse Event Form, if the event is determined to be an ADE).

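### The rule limiting reportable hypoglycaemia has no SAE exception, so a hospitalised, non-ADE hypoglycaemia outside the SH definition is reportable under one section and not under another

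*Combined protocol and SAP*

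**What the plan says.** All the relevant text is in the Adverse Events chapter of the combined protocol and SAP.

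- **Reportable Adverse Events, the list.** The section opens with "a reportable adverse event includes any untoward medical occurrence that meets one of the following criteria, as defined below" and gives four items: SH, DKA, an SAE and an ADE. Meeting any one is enough.
- **Reportable Adverse Events, closing paragraph.** "Hypoglycemia and hyperglycemia not meeting the criteria below will not be recorded as adverse events unless associated with an adverse device effect (ADE").
- **Severe Hypoglycemia.** "Hypoglycemia not associated with an ADE is only reportable as an adverse event when the assistance of another person was required". The assistance must be needed because of altered consciousness.
- **Diabetic ketoacidosis.** "DKA is reportable as an adverse event when the subject reports the following". Three conditions follow, all required: symptoms, treatment in a health care facility, and a provider's diagnosis of DKA.
- **Serious Adverse Event (SAE).** One limb of the definition reads "Requires hospitalization or prolongation of existing hospitalization". Glycaemic events are not carved out. The section ends: "A serious adverse event must be reported to the FDA as soon as possible, within a maximum of 15 calendar days".
- **ADE section.** The definition given is "Any untoward medical occurrence in a study subject which the device may have caused or to which the device may have contributed".

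**The concern.** The list treats seriousness as a separate route to reportability. The two glycaemic rules then narrow reportability for low and high glucose and let back in only events associated with an ADE. Neither mentions seriousness.

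Consider a participant admitted to hospital for hypoglycaemia who never had altered consciousness and whose event is not linked to the device. Staff working from the SAE section would complete a form and report to the FDA. Staff working from the Severe Hypoglycemia section would conclude that the event is not reportable.

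The Protocol Synopsis says the study is designed primarily to collect safety data. Serious glycaemic events just outside the SH and DKA definitions are directly relevant to an insulin-dosing system, so their recording should not depend on which section a member of staff consults.

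**Working it through.** No plan figure is at issue, so the check is textual. I applied the rules to four hospitalised events, taking the closing paragraph's reference to the criteria that follow it in two ways: *narrow* (the SH and DKA criteria only) and *wide* (all four listed criteria, including SAE).

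| Hospitalised event | ADE-associated | List item 3 and SAE section | Severe Hypoglycemia section | Closing paragraph, narrow | Closing paragraph, wide | Result |
|---|---|---|---|---|---|---|
| Hypoglycaemia outside SH | No | Reportable, FDA report due | Not reportable | Not recorded | Not excluded | Contradiction on both readings |
| Hyperglycaemia outside DKA | No | Reportable, FDA report due | Does not apply | Not recorded | Not excluded | Contradiction on the narrow reading only |
| Hypoglycaemia outside SH | Yes | Reportable, FDA report due | Excepted | Excepted | Not excluded | No conflict |
| Hyperglycaemia outside DKA | Yes | Reportable, FDA report due | Does not apply | Excepted | Not excluded | No conflict |

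**Row 1** does not depend on how the closing paragraph is read. The word *only* in the Severe Hypoglycemia section leaves no SAE route, while list item 3 and the SAE section provide one.

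**Row 2** depends on the reading. Two features favour the narrow one. First, an ADE is itself the fourth listed item, so naming it as the sole exception would be redundant if all four criteria were already meant. Second, the Severe Hypoglycemia section restates the same rule with the SH definition as the criterion and ADE as the only exception. On the other side, the list introduces all four items as criteria defined further on, the SAE definition does come after the closing paragraph, and the DKA section contains no *only*.

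**Does another section settle it?**

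- Adverse Event Definitions promises that all AEs will be documented, but subject to the rules set out after it, which leads back to the conflict.
- Observation and Recording of Adverse Events requires a form for every reported and verified AE. That does not help where the rule says the event is not to be recorded or reported as an AE.
- The Synopsis entry on periodic data collection has all support calls screened for reportable AEs against the SH and DKA definitions, and the monthly surveillance query looks for SH and DKA. Both make the narrow reading plausible in daily practice.

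No section states an order of precedence.

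**The case against.** The strongest reply is that the gap is small and partly closed elsewhere. Much of that stands.

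- **Hyperglycaemia.** A reader might infer the same flat contradiction here. The wide reading avoids it. The redundancy argument for the narrow reading is good but not conclusive, since an event *associated with* an ADE need not itself be an ADE, so the exception could have its own function. This half is an ambiguity.
- **Device-related events.** A reader might infer that the ADE exception is of no use because causality is judged on a completed AE form, or that SAE counts are biased downward for the very events the device can cause. The documents do not support this. The ADE threshold is low (possible causation or contribution), both glycaemic rules expressly keep ADE-associated events, and no section says that ADE association can be recognised only after a form exists.
- **Suspected DKA.** A reader might infer that admissions with an incomplete self-report never reach review. Adverse Event Definitions provides for contacting the participant, requesting records or contacting the physician when information on a suspected AE is inadequate, and outreach contacts carry open-ended questions.
- **A count of lost events.** One could take the expected SH count, 1,547 × 25.35/100 = 392, and apply a percentage. The percentage would have no source in the documents. In addition, 1,547 is a number of expected completers, not patient-years, and Step 3 of the sample size section gives 1,354 instead (1,354 × 25.35/100 = 343). Such a range would not measure this conflict.

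What the reply does not remove is row 1 of the table: the follow-up routes can bring the event to light, but staff then meet two rules that disagree.

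**Conclusion.** The point holds for hypoglycaemia. An admission outside the SH definition and not associated with an ADE is a reportable SAE with a 15-day FDA limit under the list and the SAE section, and not reportable under the Severe Hypoglycemia section. For hyperglycaemia outside the DKA definition the text is ambiguous. The narrow, excluding reading is the better supported, but not the only one.

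The affected events lie outside the SH and DKA definitions by construction, so the primary SH and DKA rates, their tests and the sample size are unchanged. The consequence is for completeness and consistency of SAE recording and FDA reporting. Its size cannot be derived, because the documents give no rate for hospitalised glycaemic events outside the two definitions. The conclusion rests on the wording alone and assumes no event rate. It is worth correcting because safety data are the study's main purpose, but it does not threaten the primary analysis.

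**What to change.** Reconcile the Reportable Adverse Events, Severe Hypoglycemia and SAE sections by adding the SAE route to both exceptions:

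- Closing paragraph of Reportable Adverse Events: *unless associated with an ADE or meeting the definition of an SAE*.
- Opening of Severe Hypoglycemia: limit the rule to hypoglycaemia *not associated with an ADE and not meeting the SAE definition*.

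The first clause also removes the ambiguity for hyperglycaemia. List events captured this way as SAEs, separately from the SH and DKA rates, so that the primary comparison with the literature rates keeps its definitions.

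The cost is two clauses of protocol wording, a few more AE forms and possibly a slightly higher SAE count.
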